6. DATA AND SAFETY MONITORING PLAN

A data safety and monitoring plan will be implemented for this project, following well-established procedures within KB. We will not set up an independent Data Safety and Monitoring Board because this trial is very low risk; does not include use of therapeutics; and physical risks are not anticipated. However, the progress of the research will be monitored monthly by the PI. All critical events will be reviewed by the Investigator to ensure that project methods have not been intrusive or disruptive.

The team will monitor progress, discuss concerns, problem-solve, and take corrective actions. [name] (PI) is a licensed psychologist in Colorado (#3630) and Louisiana (#1197) and will assemble a group of experts including at least one licensed mental health professional, one physician, and one biostatistician. Participants who express emotional or physical distress will be referred to their treating physician immediately. Based on our experience and demonstrated ability to conduct this type of research, we are confident we can achieve safe intervention delivery.

The data management staff will attend regular project meetings with the PI and other project staff and routinely report on the quality of the data and other outcomes of this monitoring process. Annual reports on data safety and monitoring are submitted to WIRB.

Compliance with data collection protocols will be monitored throughout data collection by the Investigators. The Investigators are responsible for reporting all adverse events to the IRBs. Only Grade 1 events are expected on this trial. Thus, adverse events will be reported annually, as required by DHHS. This report will be reviewed by WIRB. Any action taken by the IRBs or project investigators resulting in a temporary or permanent suspension of the trial will be communicated immediately by the PI to the grant program officer.

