Retention, Tracking, and Attrition: Although participants can withdraw at any time, steps will be used to minimize dropouts to ensure high internal validity. Participant progression will be tracked. Staff will use behavioral reinforcement strategies known to be effective in the behavior change literature¹⁵⁸⁻¹⁶⁰ and be trained to develop rapport with participants by communicating expectations for participants and staff. Personalizing this relationship will enable participants to be more direct about problems, providing a strong foundation for problem-solving. While drop-out rates vary among youths with SCD,^{57,161} we conservatively planned for 20% attrition. Our method of tracking and multiple contacts will help us retain some of these participants for intent-to-treat purposes, despite their discontinued app use. Participants will provide contact information for one individual who can always contact them and update contact information at each assessment. If they do not respond to email/text reminders, we will follow-up by phone. Finally, we will create a dummy coded variable for each respondent where 1=completers and 2= drop outs and test for associations with key variables in our analytic models. If bias is identified, we will control for it by adding it as a covariate.

Compensation: All participants (n=100) will be compensated to incentivize and improve study retention. A \$20 gift card will be given to the teens after each study assessment (baseline, 6-week, and 12-week) for a total compensation of \$60. Parents will be provided a \$10 gift card after each study assessment for a total of \$30.

App Use: Implementation of technology-based interventions can be challenging due to participants forgetting, fatiguing, or believing they have learned all they need to know. In order to bolster compliance with using either of the assigned app, weekly reminders to use the app will be sent to participants by text message.

3C.7.4. Safety Considerations. Participant safety is a priority. This study will include a Data and Safety Monitoring Plan (DSMP). The team will monitor progress, discuss concerns, and take corrective actions. [name] (PI) is a licensed psychologist and will assemble a group of experts including at least one licensed mental health professional, physician, and biostatistician. Participants who express emotional or physical distress will be

FIGURE 7: Schedule of Measurements

Assessment	Screening	Pre-test/Baseline	Week 6	Week 12/Post-test

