Inclusion Screener*	X			
Communication and SCD Pain Knowledge measure**		X	X	X
Pain Assessment Tool		X	X	X
SCD Transition Program Questionnaire		X	X	X
SCD Transition Knowledge Questionnaire		X	X	X
Sickle Cell Self-efficacy Scale		X	X	X
Family Cohesion Scale		X	X	X
CDC Flu IQ Questionnaire		X	X	X
App Usage			X	X
System Usability Scale			X	X

* Completed by parent only

** Completed by teen and parent

referred to their treating physician immediately. Based on our experience and demonstrated ability to conduct this type of research, we are confident we can achieve safe intervention delivery.

3C.8. Data Collection, Management, and Security. KB has used online data collection successfully in a number of studies. Study consents and pretests and posttests will be collected online via participants' personal smartphone or tablet. Surveys will be programmed using QuestionPro software on KB's secure web server to ensure a structured approach and reduce errors/missing values. All procedures will be approved by KB's IRB.

KB has considerable experience maintaining large databases and ensuring high-quality data. [name], KB's Biostatistical Manager, will supervise data management. All data will be uploaded in real-time using KB's secured network; data will be de-identified and stored in KB's secured database. Established KB protocols for quality assurance (valid ranges; internal consistency checks, etc.) will ensure high quality data. The KB data team will compile master data files. Survey and app usage data will be linked. Missing data should be limited since data is recorded electronically. Staff will identify missing responses and check that entries were not intentionally skipped. Analyses will be done on data collected. While unlikely, data may not be missing at random (NMAR). KB will assign all lost responses to extreme category and perform multiple imputation procedures that can handle various amounts of missing data and use covariates and propensity scores.

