For evaluation period, participants will be sent an email describing the study and a link to a screening survey administered on KB's secure server that assesses inclusion criteria and demographic characteristics. The online screener will take about five minutes to complete. If needed, phone recruitment and screening will also be used. After being screened, participants will receive an email to inform them of their eligibility status. Eligible participants will be scheduled for an orientation and baseline assessment, which will be conducted via videoconferencing. Participants will have the study explained and provide online consent (parent) and assent (child). After providing consent and assent, participants will attend a one-on-one orientation. During the orientation, teens will be assisted with app download, provided instructions on how to use the app, and encouraged to use the app daily. Then the baseline assessment session will be conducted via videoconferencing. Participants will complete the (online) baseline survey(s) using their personal smartphone or tablet device, which should take about 30 minutes to complete.

Participants will complete a 6-week assessment of initial changes. An invitation email and text messages containing a link to the survey(s) along with their unique password (PIN number) will be sent. Participants will complete the online survey(s) using either their tablet or smartphone; no videoconferencing will be required for the 6-week assessment.

Participants will complete a 12-week post-test assessment. Participants will meet individually with study staff via videoconference to complete the online survey(s) and a brief post-test interview.

Consenting/Assent procedures are as follows:

A parent will be present and give consent for the child during the videoconference. Children will provide assent. Eligible children will be invited to participate, consented/assented using the following procedures:

1. Research staff will send an introductory email inviting eligible parents and children to participate and follow-up with emails and telephone calls to recruit them.
2. Interested parents will go to the study website to register and complete an online enrollment form, providing contact information (i.e., name, address, telephone numbers [home and mobile phones], and email address[es]) for themselves, their child, and people who can always locate them and their child (i.e., a locator).

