3. Each parent and child will sign online consent form/assent form at the study website. If a parent or child does not consent/assent the child will not be enrolled. Participants will give their consent/assent electronically and be able to download and save (or print) a copy of the consent/assent form. The IRB-approved consent/assent forms will describe the purpose of the project, risks and benefits, and selection criteria. Participants will be informed that they have a right to withdraw from the study at any time. No additional data will be collected from participants who decide to withdraw; however, the information collected prior to withdrawal will remain in the study. All correspondence will contain the PIs' email addresses and phone numbers for invited participants to use if they have questions.

Participation in all stages of this Phase II application is entirely voluntary and subjects are free to withdraw from the project at any time without negative consequences. Furthermore, withdrawing from the study will not affect the participants' benefits. No additional data will be collected from participants who decide to withdraw; however, the information collected prior to withdrawal will remain in the study.

5B.2. Protection Against Risk. To minimize potential psychological risk, usability testing facilitators/interviewers will establish ground rules for discussion that includes an open, non-evaluative exchange of

comments and ideas. IRB-approved discussion procedures will be carried out under the supervision of senior project staff. Participants will be told that they do not have to answer any questions that make them uncomfortable and can terminate their participation at any time they wish. Notes, surveys, and data will be accessible only by research personnel. Data forms and computer records will be labeled only with participant identification number. Participant names and study identification numbers will be recorded and stored separately from the research data files.

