Any survey questions and discussion transcripts will be de-identified before being submitted for analysis and the Research Assistant will remove any references to individual names or identifier data. There are no clinical data to be captured. Responses to survey questions and participation in discussions will not reasonably place the subjects at risk of criminal or civil liability or be damaging to the subjects' financial standing, employability, or reputation. The data collected on this project will be obtained with the "use of educational tests, survey questions and interview procedures."

To protect privacy and to ensure that the participant is the person completing the app activities, KB will uniquely identify the user's smartphone/tablet based off the device's "hardware footprint". The app will upload all app activity data to the KB secured web server database.

All surveys and data collection forms will be IRB-approved and administered under the supervision of senior project staff. Participants will be told that they do not have to answer any questions which make them uncomfortable and can terminate their participation at any time they wish. Notes, surveys, and data will be accessible only by research personnel. All notes will be stored in locked cabinets; all electronic data files will be stored on KB's secure network servers behind computer firewalls, with routine backup. All identifiers will be stored in secure files and behind computer firewalls and results will be shared in aggregate form only.

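### The plan undertakes to report all adverse events but describes no systematic way of finding them, so a low count could not be read as evidence that the app is well tolerated

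*Combined protocol and SAP*

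**What the plan says.** **The promise.** Section 6 says "The Investigators are responsible for reporting all adverse events to the IRBs". It continues: "Only Grade 1 events are expected on this trial. Thus, adverse events will be reported annually, as required by DHHS". On review it says: "All critical events will be reviewed by the Investigator to ensure that project methods have not been intrusive or disruptive". The same section refers participants who express distress to their own physician and has the lead investigator assemble a group that includes a mental-health professional, a physician and a biostatistician. It defines neither an adverse event nor a critical event.

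**The schedule.** "FIGURE 7: Schedule of Measurements" has ten rows: the screener, the "Communication and SCD Pain Knowledge measure", the Pain Assessment Tool (PAT), two sickle cell knowledge questionnaires, self-efficacy, family cohesion, the influenza quiz, app usage and the System Usability Scale. The measures described in 3C.7.2 add no safety item.

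**The contacts.** Section 5B.1 says "no videoconferencing will be required for the 6-week assessment". At week 12, staff meet each teen by video for the surveys and a short interview whose content is not given (3C.7.1). Parents complete only the proxy of the knowledge measure (3C.6, 3C.7.1).

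**Leavers.** Section 5B.1 says "No additional data will be collected from participants who decide to withdraw". Section 3C.7.3 separately plans phone follow-up of people who do not answer reminders, and expects to keep some who have stopped using the app.

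**Clinical information.** Section 5B.2 says "There are no clinical data to be captured", and 5G says that no medical information will be collected.

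**The concern.** The issue is how events are found, not how often they are reported. A duty to report every event has content only if something brings events to the investigators' attention, and every route described depends on a teen or parent raising the matter unprompted.

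Section 5A.3 limits the foreseen risks to minimal psychological ones. The intervention asks 13- to 17-year-olds to monitor their pain daily (3C.4.3c), with daily notifications (3C5.1). Whether this upset anyone is the obvious safety question, and no scheduled item puts it. The SAP intends to study dropouts for signs of weakness in the app, yet no reason for leaving is collected.

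At stake are the annual report to the IRB and any later statement that the app was well tolerated. Both would rest largely on what was volunteered, and information not gathered at the time cannot be recovered afterwards.

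**Working it through.** **1. The plan's own figure.** The SAP assumes that 80% of teens have baseline and post-test results. Then 80 / (1 − 0.20) = 100, which reproduces the stated sample size. The documents give no adverse-event rate, safety sample size or safety threshold.

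**2. How many teens could be silent.** 20% of 100 is up to 20 teens without a post-test result. The documents do not divide them into formal withdrawals (no further data) and non-responders (phoned). The number about whom nothing more is heard therefore lies between 0 and 20.

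**3. Routes by which an event could surface.**

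| Route | Section | Asks about events? |
|---|---|---|
| Week-6 survey | 3C.7.1, 5B.1 | No; unattended, outcome measures only |
| Week-12 video visit | 3C.7.1 | Not stated |
| PAT at three time points | 3C.7.2, Figure 7 | Covers pain and stress; no attribution to the app and no stated safety review |
| Parent survey | 3C.6, 3C.7.1 | No; knowledge proxy only |
| Phone follow-up of non-responders | 3C.7.3 | No safety content stated |
| Expressed distress | 3C.7.4, 6 | Passive; referral, with no recording step stated |
| After formal withdrawal | 5B.1 | No data collected |

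**4. What an empty record would mean.** If all n teens are asked and none reports an event, the one-sided 95% upper limit on incidence is 1 − 0.05^(1/n):
- n = 80: 3.7%
- n = 100: 3.0% (2.95%)

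If each event comes to light only with probability q, the limit is divided by q. For n = 100 it becomes 2.95/0.5 = 5.9%, 2.95/0.25 = 11.8% and 2.95/0.1 = 29.5%. Under the plan q is unknown, so no limit can be claimed.

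**5. Chance of an empty record.** With true incidence p, at most one event per teen and independent teens, the chance is (1 − pq)^100. Both p and q are assumptions, because the documents give neither.

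| p | q = 1 | q = 0.5 | q = 0.25 | q = 0.1 |
|---|---|---|---|---|
| 1% | 36.6% | 60.6% | 77.9% | 90.5% |
| 5% | 0.6% | 8.0% | 28.4% | 60.6% |
| 10% | <0.1% | 0.6% | 8.0% | 36.6% |

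An empty record is certain only at q = 0.

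**6. Background events.** The Phase I interviews (3C.1b; only four teens, so very imprecise) gave 1.5 very bad pain episodes a week. Over 12 weeks that is 1.5 × 12 = 18 per teen, or 18 × 80 = 1,440 to 18 × 100 = 1,800 in the trial. Section 6 does not say whether these count as adverse events, or how they fit an expectation of Grade 1 events only.

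**The case against.** The strongest reply is that this is an educational app with no therapeutics and minimal risk, that no safety endpoint or tolerability claim is planned, and that several routes to detection exist. That is fair as far as it goes. Low risk is a reason not to convene a monitoring board. It does not explain how all events are to be reported when nobody is asked about them.

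Four stronger readings are tempting, and the documents do not support them:
- **That leavers are never contacted again.** Section 3C.7.3 phones non-responders and keeps some who stop using the app. Section 5B.1 stops data collection only for those who decide to withdraw, and it bars data rather than contact.
- **That about 20 teens will have no staff contact after starting the app.** Twenty is the upper end of a range that starts at 0.
- **That the safety record will be clean whatever happens.** Volunteered complaints, distress referral, critical-event review, the week-12 interview and PAT answers could each bring an event to light.
- **That review is confined to the investigator and to intrusiveness.** Section 6 contains no such restriction, and it places a physician and a mental-health professional within the monitoring plan. The fair complaint is that their part in event review is not spelled out.

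Two further points stand. Appendix E, the interview guide and the company's internal monitoring procedures are not in the supplied text, so a safety question there cannot be excluded. And a broad question about any health event would conflict with 5B.2 and 5G and would be swamped by routine sickle cell pain. The remedy must be narrower than that.

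**Conclusion.** The concern holds in this form: the plan undertakes to report all adverse events, describes no systematic ascertainment, and collects nothing after formal withdrawal. Some events may surface, but the one kind of risk the plan names will be under-recorded unless every affected family speaks up unprompted. A low or zero count cannot be read as evidence that the app is well tolerated.

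Between 0 and 20 of 100 teens may be silent after leaving. At an assumed 5% incidence, the chance of an empty record runs from 0.6% with full detection to 61% if one event in ten is detected. The incidence and detection values are illustrative. The finding itself rests on Figure 7, 3C.7.1 to 3C.7.3, 5B.1 and Section 6, and on Appendix E and the interview guide containing no such item. The change should be made, in proportion to a low-risk study.

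**What to change.** 1. Add one yes/no item with free text to the existing teen and parent surveys at weeks 6 and 12. Limit it to any problem or upset that the respondent thinks is connected with using the app or taking part in the study. Add the row to Figure 7. If Appendix E or the interview guide already has such an item, list it there.
2. Ask one optional reason-for-leaving question when a teen withdraws, and reword 5B.1 and the consent and assent text to allow it.
3. State in Section 6 that positive answers are reviewed with the physician and mental-health professional already planned.
4. Reconcile the undertaking to report all adverse events, and the expectation of Grade 1 events only, with the statements in 5B.2 and 5G that no clinical or medical information is collected. Define an adverse event for this study and say whether ordinary sickle cell pain episodes count.

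Cost: one short item on at most 400 surveys (100 teens and 100 parents, two time points), some disease-related answers to sort, and a minor consent and IRB wording change. The narrow wording keeps the number of positive answers down, and the reviewers are already planned.

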7. INCLUSION OF WOMEN AND MINORITIES

Females and minorities (African Americans and Hispanics) will be included in this research as part of the sample of patient participants.

SCD rates in African Americans and Hispanics are far higher than in Whites. It is estimated that SCD affects to 100,000 Americans. Sickle cell disease occurs in approximately 1 in 365 African Americans; 1 in 16,300 Hispanics, and nearly 1 in 400,000 Whites. Thus, the sample of participants in the proposed research will contain the following 3 racial/ethnic groups: Black, Hispanic, and White. We will attempt to recruit: 97% African American; 2% Hispanic (any race); and 1% White.

During the recruitment process, the Project Coordinator will screen for participants using IRB-approved protocols for screening based on gender, race, and ethnicity. If the Project Coordinator finds that we are over-recruiting a particular gender or racial or ethnic group, we will place them on a waiting list until we have recruited an adequate number of targeted participants. See Targeted Enrollment Table.

Sample size: The primary outcome is detecting a positive change on the knowledge acquisition questionnaire (communication skill and pain identification). To be conservative, we assumed that 80% of those offered the app will have baseline and post-test results. Our sample size of 100 allows for up to 20% dropouts. We expect results similar to those found by Barakat et.al.¹⁵⁹ on our secondary outcome measures (which were similar to ours). We used their results to derive our nonparametric sample sizes on SCD disease-specific and transition knowledge, and family cohesion. For the transition knowledge construct, assuming the correlation before-to-after is 0.5, the sample size is N=22, using power of 80% and a Bonferroni corrected Type I error of 0.0167. For disease-specific knowledge, the sample size necessary to achieve 80% power is 76 participants, using the same assumptions (Type I error of 0.0167). For the third outcome (i.e., family cohesion), if we assume 80 participants at all time points, then the power is somewhat lower since the sample size required to achieve 80% power is 132 (mean difference between post-test and baseline was 6.51 with a pooled standard deviation of 22.8). For this outcome, the power with 80 participants is 54%. We weighed the importance of the first two outcomes (disease-specific and transition knowledge) relative to the increase in cost and duration to increase the sample to 165 (i.e., 132 plus dropouts up to 20%) to account for the single-item family cohesion variable. We felt that having greater than 50% power for family cohesion and sufficient power for the participant-related measures (80% for SCD disease-specific and transition knowledge), we would not increase the sample size by 65% (i.e., from 100 to 165) in order to achieve 80% power for family cohesion. We have nevertheless left it in, because we respect its importance. As a Phase II study, we believe that we can accept less power on that single measure given consistency of outcomes will drive further evolution of this product.

Analyses: There are 2 aims that will be evaluated (AIMs 2 and 3). As a Phase II SBIR, the analyses are heavily descriptive in nature for this trial. Means (standard deviations), medians (interquartile range), distributions, frequencies and percentiles, etc. will be used to characterize the outcome measures.

For Aim 2 (Usability), 14 users are needed to identify any problems that impact $\geq 15\%$ of users at a 90% chance of detection ($\log(1-.90)/\log(1-.15)$). Data on applied formative research suggests that 5 participants is sufficient to identify likes/dislikes and potential errors; thus, the power to detect Level 1 severity usability errors should be more than sufficient with $n=14$.¹⁶⁷ Similar to Phase I, usability outcomes will also include program satisfaction ratings with regards to design, appeal, and functionality. Each concept will be rated on a 5-point Likert scale. Means will be calculated and an average of 67% or higher will be considered acceptable. We will examine mean scores, changes in mean scores, and variation within geographical location. The SUS will serve as the primary criterion for measuring usability.^{113,121,122} Further, we will look for outliers to assess if there may be specific characteristics of users who have or develop problems as the processes evolve.

Effectiveness (AIM 3) is critical to product development and will evaluate whether *Pinpoint* increases communication and pain identification knowledge. Means (standard deviations), medians (interquartile range), distributions, frequencies and percentiles will be used to characterize the primary outcome measure. We will test the within person change over time for knowledge acquisition, SCD disease-specific and transition knowledge, SCD self-efficacy, and family cohesion. Linear regression will assess the effects of age, **biologic sex**, and education. Parents will complete a proxy version of the primary outcome; child and parent-report agreement will be assessed using intra-class correlations and median difference tested using Wilcoxon significance tests. Kolmogorov-Smirnov tests will assess for normal score distribution.

Characteristics of dropouts and/or noncompliant individuals will be examined to shed light on potential weaknesses of the app (differential dropout overall or within certain subgroups). Utilization data will be examined to understand the acceptability and intensity of interactions with the app. The penetration of the app into this at-risk population is very important in understanding potential impact. Complier average causal effect models¹⁶⁸ will be used to examine the intensity of the app's utilization. Mediation models using the latest

bootstrapping methods^{169,170} will be examined to provide evidence that the changes induced by the treatment effects are consistent with the changes being mediated via the app.

As a sensitivity analysis to demonstrate discordant validity, we will perform the same analysis as on the primary outcome, using the number of correct answers in the CDC Flu IQ (i.e., nonequivalent dependent variable). This outcome should not be impacted by the intervention and we expect to see no change in the mean number correct. Although failure to show a difference is not evidence for no difference, the discordant effect size should provide additional information that the primary results are consistent with an intervention effect.

Evidence for Scientific Rigor and Potential Limitations. The study has numerous strengths, few limitations, and is scientifically rigorous. The study is theory-driven (i.e., User-centered Design and Social Cognitive theories). Formative data will incorporate multiple stakeholder input. The programming approach will be multi-model and evidence-based (i.e., ADDIE Model, MDA framework, AGILE programming) resulting in a systematic, flexible, and cost-effective approach. Sample sizes are sufficient and supported by the literature. Effectiveness will be evaluated in a within-subjects design which allows for sufficient power (i.e., statistical inference with fewer subjects), efficiency (i.e., quicker trial completion), and longitudinal analysis (i.e., individual changes over time). The study team and environment are strong. Potential limitations are: (1) difficulty recruiting; (2) sources of bias; and (3) lack of control group. We have tried to reduce their impact. We will work closely with the EAB and PAB to maximize recruitment. Our primary outcome measure is new, but we are using a rigorous approach to scale development. Self-report instruments are open to bias, however the use of validated measures is a strength. Limitations of no control group are lessened via the use of a time-series design for outcome changes and testing of a nonequivalent dependent variable.

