6-week interim assessment: Participants will complete interim assessments of initial changes (i.e., teens to complete all measures; parent to complete the single proxy measure assessing their child's knowledge acquisition). An invitation email and text messages containing a link to the surveys along with their unique password (PIN number) will be sent. Participants will complete the web-based surveys using either their tablet or smartphone; no video meeting will be required. Participants who do not complete the surveys within 3 days will receive an email and text reminder (and 3 more reminders at 3-day intervals if still not completed).

12-week post-test assessment: Participants will complete a post-test assessment via videoconference. They will meet individually with a study staff to complete the online surveys and a brief post-test interview.

3C.7.2. Outcomes: Baseline, Interim, and Post-test Measures. The baseline, 6-week interim, and 12-week post-test surveys will use a measure created by the investigative team and EAB as the primary outcome (i.e., knowledge acquisition for communicating about pain and types of pain). Secondary outcomes will be the app Pain Assessment Tool (PAT) and validated measures of SCD knowledge, disease self-efficacy, and family cohesion. Surveys should take 30 minutes to complete (see **Figure 7** and **Appendix E**).

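### The 0.0167 level allows for three secondary outcomes but the SAP tests four, and no calculation covers the primary outcome

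*Combined protocol and SAP*

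**What the plan says.** The sample size paragraph of the SAP opens with the primary: "The primary outcome is detecting a positive change on the knowledge acquisition questionnaire". It assumes that 80 of 100 participants will have both baseline and post-test results. It then turns to a cited earlier study: "We used their results to derive our nonparametric sample sizes", for disease-specific knowledge, transition knowledge and family cohesion. Transition knowledge (N=22) and disease-specific knowledge (N=76) are sized "using power of 80% and a Bonferroni corrected Type I error of 0.0167". Family cohesion, called the third outcome, needs N=132 and has 54% power with 80 participants, based on this input: "mean difference between post-test and baseline was 6.51 with a pooled standard deviation of 22.8".

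The Analyses paragraphs of the SAP give a longer list under Aim 3: "We will test the within person change over time for knowledge acquisition, SCD disease-specific and transition knowledge, SCD self-efficacy, and family cohesion". No significance level or multiplicity rule appears there. Protocol section 3C.7.2 defines the secondaries more widely still: "Secondary outcomes will be the app Pain Assessment Tool (PAT) and validated measures of SCD knowledge, disease self-efficacy, and family cohesion". The same section lists seven gamified PROMIS domains as secondary outcomes and plans to gamify three more. None of these is in the SAP's test list.

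Protocol section C.10 and the closing section of the SAP both state: "Sample sizes are sufficient and supported by the literature".

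**The concern.** A Bonferroni level is tied to the number of tests it covers. Here the divisor is three and the tested secondaries number four. Self-efficacy has neither a share of alpha nor a sample size. A reader who takes 0.0167 from the sizing paragraph into the results would believe that the secondaries are held to 5% together when they are not.

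The primary is in a weaker position. It has no significance level, no effect size, no standard deviation and no power, and its questionnaire has still to be developed (3C.7.2). The reader cannot tell at what p-value the primary result counts as positive, or how large a change 80 completers could be expected to detect.

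**Working it through.** **Inputs.** From the SAP sample size paragraph: level 0.0167, 80% power, before-after correlation 0.5 (stated for transition knowledge and carried over for disease-specific knowledge), family cohesion change 6.51 and SD 22.8, N=132 and 54% for family cohesion, N=76 for disease-specific knowledge, 80 completers. From the SAP Analyses paragraphs: five tested outcomes, one primary and four secondary.

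**1. The divisor.** 0.05/3 = 0.016667, which rounds to 0.0167. Three outcomes are sized and family cohesion is called the third, so the divisor is three.

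**2. Reproducing the plan's own figure.** Family cohesion is the only sized outcome with printed inputs. With correlation 0.5, the SD of the change is 22.8 × √(2 × (1 − 0.5)) = 22.8, so the standardised change is 6.51/22.8 = 0.2855. A paired t-test (noncentral t) at 0.0167 gives:

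| Calculation | N for 80% power | Power at n=80 |
|---|---|---|
| Two-sided paired t | 132 | 54.5% |
| One-sided paired t | 111 | 65% |
| Two-sided rank test (paired t adjusted by efficiency 3/π) | 139 | 52% |
| SAP | 132 | 54% |

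Only the two-sided paired t matches. The correlation of 0.5 is not restated for this outcome, but 0.4 would give N=157 and 0.6 would give N=106, so 0.5 is what was used. The figure is therefore not a nonparametric one. N=22 and N=76 cannot be checked, because their means and SDs are not printed.

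**3. Family-wise error if 0.0167 is used for all four secondaries.**
- Upper bound: 4 × 0.016667 = 0.0667.
- Independent tests: 1 − (1 − 0.016667)⁴ = 0.0650.
- Equicorrelated normal statistics, correlation 0.5 (assumed, by simulation): about 0.057.

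**4. What 80 completers can detect on the primary.** Two-sided paired t at 0.05: 80% power at a standardised change of 0.317. Power is 42% at 0.2, 60% at 0.25 and 76% at 0.3. If 0.0167 applied to the primary as well, the detectable change would be 0.368. These changes are illustrative, as the documents give none for the primary.

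**5. Power under the corrected divisor.** Plain Bonferroni over four gives 0.05/4 = 0.0125, which is also Holm's worst case. For disease-specific knowledge, the standardised change is back-solved from N=76 as 0.378 to 0.381.

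| Outcome, n=80 | At 0.0167 | At 0.0125 |
|---|---|---|
| Family cohesion | 55% | 50% |
| Disease-specific knowledge | 82–83% | 79–80% |

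**6. Error across both families.** With the primary at 0.05 and the four secondaries under Holm at 0.05, the bound is 0.05 + 0.05 = 0.10. If the tests are independent it is 1 − 0.95 × (1 − 0.0125)⁴ = 0.097.

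**The case against.** The strongest reply is that 0.0167 occurs only in the sizing text. The analysis section adopts no level and no correction, and the SAP says: "As a Phase II SBIR, the analyses are heavily descriptive in nature for this trial". On that reading there is no analysis rule to fail. This stands in part: every family-wise figure above is conditional on carrying 0.0167 into the analysis. It does not remove the point, since the SAP commits to testing five outcomes and the only level it prints allows for three.

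It is also fair that the excess is small, and smaller still when outcomes from the same teenagers are correlated. Nor could an effect size in score units be known for an instrument not yet written. A detectable change in SD units, however, needs neither the instrument nor its SD.

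The proposed scheme allows up to 10% across all five tests, whereas 0.0167 on all five would allow 5 × 0.016667 = 8.3%. That is true. Treating the primary and the secondaries as separate families is a convention, and the resulting total should be stated openly.

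On the word nonparametric, family cohesion is a single five-point item, so a rank method is defensible. The figures could be changed to suit the word, not only the reverse.

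Finally, a reader might take protocol section 3C5.1, which speaks of a sample large enough to detect changes in primary and secondary outcomes, as a claim of shown power. It describes where recruitment resources will go. The claim open to criticism is the flat statement in C.10 and in the SAP's closing section.

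**Conclusion.** The point holds at modest size. The divisor of three does not match the four secondaries that the SAP tests. If 0.0167 is used for those four, error is at most 6.7% against an intended 5%. The second part matters more: no calculation supports the adequacy of N=100 for the primary, although the plan asserts adequacy without exception.

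The result assumes two-sided testing, which is inferred from the family cohesion figures, and 80 completers. Because the SAP speaks of a positive change, a one-sided primary test is conceivable; at one-sided 0.05 the detectable change would be 0.28.

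Two stronger readings are not supported. A reader might infer that the trial's false-positive rate is 10% or more as planned; that requires levels for self-efficacy or the primary that the documents never state. A reader might also infer that the trial is underpowered for the primary. With no effect size given, its power is unknown, not shown to be low. Likewise, N=22 and N=76 are unverified, not wrong.

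**What to change.** In the SAP:

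1. Replace 0.0167 with Holm at overall 0.05 across the four secondaries in the test list: disease-specific knowledge, transition knowledge, self-efficacy and family cohesion.
2. State whether the Pain Assessment Tool domains are descriptive only or join that family. If they join, the family size and the power figures must be redone.
3. State that the primary, the baseline to week 12 change in the teen's knowledge score, is tested alone at two-sided 0.05, and that 80 completers give 80% power for a standardised change of about 0.32.
4. Limit the adequacy sentence, in protocol section C.10 as well as in the SAP, to outcomes with a stated calculation.
5. For family cohesion, either drop the word nonparametric or refigure for a rank test (about N=139, and 52% power at n=80, at the present 0.0167).

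The cost is wording and no extra participants. In Holm's worst case, power at n=80 falls from about 55% to 50% for family cohesion and from 82–83% to 79–80% for disease-specific knowledge, the latter resting on the unverified N=76. The SAP should also say that error is held at 5% for the primary and 5% within the secondaries, and can reach 10% across the two.
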